Appendix 2 – Consent form

Filed as a separate document

Appendix 3 – Initial form

Initial form

•••

Inclusion and exclusion criterias :

Inclusion criteria	Exclusion criteria		
Age ≥ 18 ans	Contraindications to Levetiracetam		
	 Psychiatric history (depression, psychosis, 		
	risk of suicide)		
	History of hypersensitivity (anaphylaxis,		
	angioedema, skin reaction) to LEV		
Transient neurological	Contraindications to Topiramate		
symptoms	History of hypersensitivity to TPM		
	Glaucoma		
	History of urinary lithiasis		
Subdural hematoma	Known epilepsy or seizure before current subdural		
	hemorrhage		
	Taking an antiepileptic		
	Intracranial pathology other than SDH		
	(subarachnoid hemorrhage, intraparenchymal		
	hemorrhage, neoplasia)		
	Pregnancy or planning to be		
	Inability to carry out the necessary follow-ups for		
	the study		
	Refusal of the attending physician		

Demographic datas :

Data type	Answers	Specification	Specifications
		types	
Age			
Sex			
Dominant hand			
(Right or left)			
Tobacco		Active, ceased,	
		never	
Alcohol		Type et	
		quantity	
Drugs		Type et	
		quantity	

High blood pressure	Adequate	
	control	
Diabetes	With or	
	without insulin	
	Type 1 or 2	
Dyslipidemia		
Auricular fibrillation		
Coronary disease	Event types	
Peripheral vascular	Location	
disease		
Migraines	With or	
	without aura	
	Aura type	
Past stroke, TIA	Event type	
Past SDH	Location	
	Past TNS	
Past intracranial	Туре	
injury	Treatment	
Past intracranial	Indication	
surgery	Туре	
Antiplatelet used	Indication	
	Туре	
Anticoagulant used	Indication	
	Туре	

SDH characteristics :

Characteristics	Answer type	Answers	Specifications
SDH type	Homogeneous		
	Laminar		
	Separated		
	Trabecular		
SDH location	Droit, gauche ou		
	bilatéral		
SDH cause	Traumatic or others		
SDH thickness	Millimeters		
Median line shift	Millimeters		
Initial Glasgow score	3-15		
Drainage surgery	Yes/no		
Surgery location	Right, left or both		
Associated subarachnoid	Yes/no		
hemorrhage	Location		

	TNS	characteristics	:
--	-----	-----------------	---

Characteristics	Answers	Specification types	Specifications
Visual symptoms		Location	
		Visual loss	
		Flash, llight	
Speech symptoms		Aphasia	
		Dysarthria	
		Mutism	
Cerebellar symptoms		Balance disorder	
		Nausea / vomiting	
		Dizziness / vertigo	
Motor symptoms		Paresis / paralysis	
		Clonic movements	
		Change in tone	
Sensory symptoms		Hypoaesthesia	
		Paresthesia	
Altered state of		Duration	
consciousness			
Duration of symptoms		Seconds/minutes	
Number of episodes		Per unit of time	
Symptom migration		How long	
		From what place to what	
		place	
Stereotypy of		If not: try to distinguish	
symptoms		the different episodes	
Prodrome		How long before the	
		episode	
		Type of symptoms	
Postictal		Duration	

Other comments :

Follow-up form

Part 1 – Neurological symptoms

Persistence of transient neurological symptoms? Yes $\Box~$ No $\Box~$

- If no : go to part 2.
- It is still important to validate all types of neurological symptoms with the patient in order to be sure that they are absent.

Characteristics	Answers	Specification types	Specifications
Visual		Location	
symptoms		Visual loss	
		Flash, llight	
Speech		Aphasia	
symptoms		Dysarthria	
		Mutism	
Cerebellar		Balance disorder	
symptoms		Nausea / vomiting	
		Dizziness / vertigo	
Motor		Paresis / paralysis	
symptoms		Clonic movements	
		Change in tone	
Sensory		Hypoaesthesia	
symptoms		Paresthesia	
Altered state of		Duration	
consciousness			
Duration of		Seconds/minutes	
symptoms			
Number of		Per unit of time	
episodes			
Symptom		How long	
migration		From what place to	
		what place	
Stereotypy of		If not: try to distinguish	
symptoms		the different episodes	
Prodrome		How long before the	
		episode	
		Type of symptoms	
Postictal		Duration	

TNS characteristics :

Other comments:

Part 2 – Side effects				
Was the antiepileptic treatment discon If yes, why ?		ient? Y	es 🗆 No	
Has the dose already been changed dur (Do not ask for the patient's dose in order to	• •	llow-up ?	Yes [□ No □
Are there any missed doses ? Yes □ If yes, at what frequency ?	No 🗆			
Possible side effects				
Туре	Yes/no	Туре	CTCAE grade	Specifications
Fatigue/sleep				
Appetite/weight				
Gastrointestinal symptoms				
Psychiatric symptoms				
High blood pressure/orthostatic				

Other side effects (specify CTCAE grade) :

Change in behavior/irritability

Other comments:

hypotension

Headaches

Paresthesia

Dizziness/vertigo

Appendix 5 – Participant notebook

Notes section

Neurological symptoms

- We are looking for transient neurological symptoms (lasting less than 60 minutes).
- To complete the table types of neurological symptoms:
 - A. Visual symptoms
 - Specifications :
 - 1. Visual loss
 - 2. Light flash
 - 3. Sparkles
 - 4. Other (Specify)

B. Sensory symptoms

- Specifications :
 - 5. Numbness
 - 6. Loss of sensation of the skin
 - 7. Other (specify)
- C. Vertigo/dizziness
 - Specifications :
 - 8. Spinning part
 - 9. Impression of turning on oneself
 - 10. Other (specify)

D. Nausea and vomiting

- E. Gait disturbances
 - Specifications :
 - 11. Balance disorders such as when consuming too much alcohol
 - 12. Other (specify)

F. Motor symptoms :

- Specifications :
 - 13. Paralysis or sudden weakness
 - 14. Abnormal involuntary movements of a limb
 - 15. Other (specify)
- G. Speech disorder :
 - Specifications :
 - 16. Inability to understand others
 - 17. Inability to speak
 - 18. Inability to articulate properly
 - 19. Other (specify)
- H. Loss of consciousness
- I. Others

• Specify in : Other comments

Date and time of	Type of symptoms	Description		
the event				
	Type of symptoms (A-B-C-D-	Duration of symptoms (seconds):		
	E-F-G-H-I):			
		Onset of symptoms:		
		🗆 Sudden		
		🗆 Gradual		
	Specifications (See those	Other comments :		
	proposed under the type of			
	symptom) (1-2-3):			
	•••			

Side effects

- Try to answer the questions in the table once every two weeks, even if no new symptoms have arisen.
- If bothersome or severe symptoms: notify a member of the research team, the dose could be adjusted or discontinued.
- List of symptoms that could occur:

A) In general:

- 1. Fatigue
- 2. Dizziness
- 3. High blood pressure
- 4. Skin rashes
- 5. Hair loss
- 6. Fever
- 7. Joint pain
- B) Intestinal:
 - 1. Weight loss
 - 2. Appetite loss
 - 3. Abdominal pain
 - 4. Nausea and vomiting
 - 5. Diarrhea

- 6. Gastroesophageal reflux disease
- C) Urinary:
 - 1. Urinary infection
 - 2. Kidney stones
- D) Neuropsychiatrics:
 - 1. Fatigue
 - 2. Anxiety
 - 3. Irritability
 - 4. Agressivity
 - 5. Agitation
 - 6. Emotional lability
 - 7. Psychosis
 - 8. Depression
 - 9. Memory impairment
 - 10. Confusion
- E) Neurologics:
 - 1. Headaches
 - 2. Gait disturbance, loss of balance
 - 3. Numbness
- F) Infectious:
 - 1. Sinus infection
- G) Ocular:
 - 1. Glaucoma
- H) Others:
 - 1. Specify

Date	Symptoms description	Characteristics	
	Type of symptoms (ex: A3):	Intensity (mild-moderate or severe) :	
	If category Others (H), please specify:	Frequency (rarely, sometimes, often) :	
	•••		

Other comments

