All adult patients presenting to any of the participating centers with transient neurologic symptoms in the setting of cSDH. The study will be multi-center and Sherbrooke will be the coordinating center.

Patients selection – sampling

- All patients presenting to one of the participating centers with transient neurological symptoms in the context of cSDH.
- Convenience non-probability sampling.
- Systematic sampling, recruiting all patients presenting at one of the participating centers, regardless of the time of admission (night, weekend). As all patients presenting with TNS in the setting of cSDH will be eligible for the study, the sample should be representative of the population. Of course, they will be included according to their willingness to participate in the study, so a bias of voluntarism is unmissable.

Inclusion criteria

- ≥ 18 years old
- Chronic subdural hematoma
- Transient neurological symptoms (Sensory, motor, cerebellar or speech symptoms, lasting 6 hours or less)
- Initial negative EEG

Exclusion criteria

- Contraindications to Levetiracetam
 - Psychiatric history (major depression, psychosis, risk of suicide)
 - History of hypersensitivity to LEV (anaphylaxis, angioedema, skin reaction)
- Contraindications to Topiramate
 - History of hypersensitivity to TPM
 - o Glaucoma
 - Past nephrolithiasis
- Known epilepsy or seizure before the current subdural hemorrhage
- Actual take of antiepileptic
- Intracranial pathology not caused by SDH (intra-parenchymal hemorrhage, neoplasia)
- Pregnancy or planning to be

- Inability to carry out the necessary follow-ups for the study
- Refusal of the attending physician

Sample size

The studies directly concerning our subject being few or even zero, we decided to calculate our sample size based on two calculations and two types of data (which do not perfectly represent our variables, each in their own way) in order to optimize our chances of obtaining a size approaching the one we need for adequate power.

Based on the means and standard deviations of reduction in cortical depressions with TPM and LEV in the fundamental studies previously described^{24,25}, it is possible for us to calculate the sample size that should allow us to establish a significant difference between our groups, if possible.

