Our collection data will take the form of a questionnaire. However, the characterization of neurological symptoms requiring some training, in order to be able to adequately distinguish relevant neurological symptoms (those transient likely caused by SDH) from those unrelated to SDH, the main measuring instrument will be a medical evaluation by a person trained in neurology or neurosurgery. This assessment will be based on a questionnaire (appendix 4), so as not to omit the assessment of all areas relevant to the study. Our study being the first on the subject, no questionnaire already approved in other studies can be used. For these reasons, we have constructed a questionnaire including a part on TNS and another on side effects. Doctors or residents evaluating patients won't forget items and will also be encouraged to further specify the various positive items found during the evaluation.

During the initial visit, a standardized questionnaire including demographic data, characteristics of cSDH and transient neurological symptoms will be completed by a member of the research team using the hospital and patient record (appendix 3). This questionnaire will be administered by a physician, resident or research nurse. We consider that characterization of the current episode at the initial visit will not require full training in neurology or neurosurgery. Indeed, the patient will have already been seen closely by a neurologist or neurosurgeon who will have considered TNS as relevant and secondary to the SDH. However, before administering this questionnaire, the nurse will receive a training, which will be given by a member of the research team.

During follow-ups, by telephone or in clinic, the patient will have in hand his research notebook (appendix 5) in which he will have made a calendar of neurological episodes

that have occurred, or side effects noted. This notebook will limit recall bias and will be analyzed as a secondary outcome, in order to compare the reliability of the information noted by patients with that reported by doctors. Subsequently, an assessment by a resident, neurologist or neurosurgeon will be done using the form described above (appendix 4).

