therapeutic doses according to the protocol below. A notebook containing the information discussed, the contact information and forms (appendix 5) for weekly monitoring of neurological symptoms and side effects will be given.

In parallel, after starting the treatment (TPM or LEV), two other daily EEGs will be performed. If an EEG is positive, there will be no further EEG needed. Additionally, if an EEG is positive, the patient will remain in the same treatment group, however, a subanalysis may compare the correlation between EEG and NESIS score results. In addition, brain magnetic resonance imaging will be recommended for patients with three negative EEGs to rule out an alternative diagnosis, such as transient ischemic events. This test is already part of the usual assessment of transient neurological symptoms with negative EEG and therefore does not represent an additional test for patients. However, this examination will be at the discretion of the clinician, depending on the clinical relevance and availability of the examination.

Electrocorticography

If the patient has TNS preoperatively, the installation of electrocorticography electrodes in the subdural space will be suggested. We anticipate that approximately 5 to 10 patients out of the 56 enrolled will be eligible and be offered this option. This step is optional and will not influence subsequent medical treatment. However, it will help to demonstrate the existence of propagated cortical depolarizations and potentially prove the effectiveness of a non-invasive screening strategy. If the patient agrees, two ECoG strip electrodes will be inserted into the subdural space along with the installation of the subdural drain during the surgery. The electrodes will be located at the level of the upper temporal line and oriented anteroposterior in order to cover the frontal operculum as well as the inferior parietal lobule. This procedure is identical to that carried out routinely in the surgical assessment of patients with epilepsy. The patient will then be transferred to the EEG monitoring unit where a surface EEG and a bi-frontal near infrared spectroscopy monitor will be installed. The patient will then be monitored continuously until at least 5 episodes of TNS are recorded, or for a maximum of 72 hours. The electrodes will then be removed by traction at the bedside and a stitch will be performed under local anesthesia. The data will be analyzed by an epileptologist.

Intervention

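### The participant notebook asks for episodes under 60 minutes, while the inclusion criterion counts episodes of up to 6 hours

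*Protocol*

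**What the plan says.** Two duration limits for the same symptoms stand in the protocol.

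- Inclusion criteria: "Transient neurological symptoms (Sensory, motor, cerebellar or speech symptoms, lasting 6 hours or less)".
- Appendix 5, Neurological symptoms, the instruction to the patient: "We are looking for transient neurological symptoms (lasting less than 60 minutes)".

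The section on the measuring instrument gives the notebook its role. At phone and clinic follow-ups "the patient will have in hand his research notebook (appendix 5) in which he will have made a calendar of neurological episodes". It adds that "This notebook will limit recall bias" and that the notebook "will be analyzed as a secondary outcome, in order to compare the reliability of the information noted by patients with that reported by doctors". The section on the initial meeting says that "forms (appendix 5) for weekly monitoring of neurological symptoms and side effects will be given".

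The notebook is not the main source for efficacy. The same measuring-instrument section says "the main measuring instrument will be a medical evaluation by a person trained in neurology or neurosurgery", and Table 3 names that assessment as the instrument for resolution, frequency and duration. The follow-up form has no upper limit on duration. It tells the assessor to go through all symptom types even when the patient reports none.

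**The concern.** The notebook's limit is the only guidance on duration that a patient receives in it, and it is shorter than the one used for enrolment. A patient enrolled with 90-minute episodes could reasonably conclude that a further 90-minute episode is not wanted.

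Two uses of the notebook would suffer.

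1. **Comparison with the doctors' report.** One source is limited to under 60 minutes and the other has no limit. An episode of 1 to 6 hours that the doctor elicits and the notebook omits would count as poor patient reporting, although the patient did what the form asked.
2. **Protection against recall bias.** For these longer episodes the calendar gives no written record, and the assessor must rely on memory. The section on sampling bias control itself notes that confusion and neurocognitive disorder are common in this population.

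Where an assessor does rely on the calendar, follow-up also stops matching baseline. The baseline questionnaire "will be completed by a member of the research team using the hospital and patient record (appendix 3)", on a form without the 60-minute limit.

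**Working it through.** The protocol states no figure to reproduce here. The check compares the texts and then asks how far the gap can reach.

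**Limits by instrument**

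| Place in the protocol | Used for | Duration limit |
|---|---|---|
| Inclusion criteria | Eligibility | 6 h or less = 360 min |
| Appendix 3, initial form | Baseline TNS | None |
| Appendix 4, follow-up form | Resolution, frequency, duration | None |
| Appendix 5, notebook | Calendar; comparison with doctors | Under 60 min |

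Episodes from 60 to 360 minutes meet the protocol's definition but fall outside the notebook's.

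**Time over which memory would have to serve.** Follow-ups are at week 2 and months 2, 4 and 6. Taking 1 month = 4.345 weeks:

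- week 2 to month 2: 2 × 4.345 − 2 = 6.7 weeks;
- month 2 to month 4, and month 4 to month 6: 2 × 4.345 = 8.7 weeks each.

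**Frequency.** Let q be the share of a patient's episodes that last 60 minutes or more, and f the true weekly number, the same at baseline and follow-up. A calendar kept as instructed shows f(1 − q). The apparent relative reduction is [f − f(1 − q)] / f = q. The protocol gives no value for q, so the possible range is 0 to 1.

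An example with assumed durations of 20, 20 and 90 minutes each week and no true change (q = 1/3):

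- baseline: 3 per week, mean (20 + 20 + 90)/3 = 43.3 min;
- calendar: 2 per week, mean 20 min;
- apparent reduction: 1 per week (33%) and 23.3 min (23.3/43.3 = 54%).

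**Difference between arms in mean duration.** The direction is not fixed. Two assumed cases, each with one episode in four lasting 60 minutes or more:

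| Case | Arm A (min) | Arm B (min) | Means, all episodes | Difference | Means, under 60 min only | Difference |
|---|---|---|---|---|---|---|
| 1 | 20, 20, 20, 120 | 40, 40, 40, 100 | 45 and 55 | 10 | 20 and 40 | 20 |
| 2 | 20, 20, 20, 100 | 20, 20, 20, 120 | 40 and 45 | 5 | 20 and 20 | 0 |

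In the first case the omission doubles the difference; in the second it removes it. These examples show the mechanism and do not estimate the trial's bias. All of them assume that the calendar is the only source, which is the worst case.

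**The case against.** The best defence is that the notebook is a secondary aid. A person trained in neurology or neurosurgery assesses the patient at each follow-up, on an uncapped form, with every symptom type checked. A long episode missing from the calendar can still be found by questioning. Baseline and follow-up forms use the same TNS table, so the planned comparison is like with like unless an assessor copies the calendar without asking further. The notebook describes what is sought and does not forbid longer entries; it also has a duration field and space for comments. Finally, the notebook-versus-doctor comparison appears in one sentence and is absent from the listed secondary outcomes, Table 3 and the Statistics section.

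Most of this stands, and it limits the weight of the point. The primary outcome is largely protected, and the effect on frequency and duration is indirect. It does not remove the contradiction. The comparison with the doctors' report is planned, and the unequal limits bear on it directly. Questioning after 6.7 to 8.7 weeks without a written entry relies on the recall that the notebook was meant to support. The section on the collection method also says that, after the initial record review, the remaining information comes from the patient or family, so what the patient noted is likely to influence the answers.

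**Conclusion.** The concern holds. The protocol uses two incompatible duration limits for the same symptoms, and the shorter one is printed on the form that patients keep at home.

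- **Direct effect:** disagreement between notebook and doctor that is produced by the forms, if any episodes of 1 to 6 hours occur and patients follow the notebook. The inclusion criterion expressly allows for such episodes.
- **Indirect effect:** a weaker record of TNS frequency and duration, and a mismatch with baseline, only where the assessor draws on the calendar.
- **Primary outcome:** largely protected by the clinician's form.

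The size cannot be stated, because it depends on the share of episodes lasting 60 minutes or more and on how far patients and assessors follow the notebook. The protocol gives neither. This is a moderate point that should be corrected; it does not threaten the main comparison.

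**What to change.** Reconcile the notebook line in Appendix 5 with the inclusion criteria. Either of two changes does this.

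- **Delete the limit**, so that the line reads, for example: *Please record every transient neurological episode, with its duration.* I would prefer this, because it also matches the uncapped follow-up form and leaves any duration rule to the analysis.
- **Replace the limit** with the 6-hour limit of the inclusion criteria.

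The notebook already has a duration field, so no new field is needed. The follow-up form's question on persistence should stay without a duration limit.

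The cost is one line in Appendix 5 and a replacement page for notebooks already handed out. If some patients have already used the present version, the notebook-versus-doctor comparison should be reported separately for episodes under 60 minutes, where both sources were asked for the same thing.
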